## 3 RECRUITMENT AND SCREENING

### 3.1 Identify the expected number of individuals screened and the expected number of individuals consented/enrolled to reach your target sample size. If multi-site, break the total down per study site. If multi-year, break the total down per study year.

**Aim 1 - Qualitative Review:** We will sample individuals from 4 groups (n=3/group) for a total of 12 participants. Our first two target groups are already identified via our already committed SMAB, close ties to the CRAFT trained counseling community, our status in the addiction professional networks, and access through professional listservs. We therefore anticipate filling our focus groups expediently with a 1 in 2, or 1 in 3, chance of targeted participants being eligible after screening and accepting the invitation to participate. As such, we expect to screen no more than about 40 individuals to reach our target sample of 12.

**Aim 2 - Training Intervention:** We will enroll 15 participants per study arm, resulting in enrollment of a total of 45 participants in the study period (6-months). Our previous family training pilot study (also with a total of 45 participants in the same project timeline) experienced a large drop off during recruitment. Although 1275 individuals began the screening process in that previous study, only 129 completed a consent form online, and only 35% of these potential participants completed the entire informed consent process, were randomly assigned and began the intervention. Given this experience with online recruitment procedures, it is possible that around 1300 participants will need to initiate the screening process in order for us to recruit, consent, enroll, and randomly assign 45 participants. We will continue to recruit via a waitlist (facilitated by online Alchemer surveys) after we have reached our goal of 45 enrolled participants. This waitlist will enable us to reach out to other eligible participants in the event that someone drops off before the baseline survey and start of intervention.

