### **Aim 2- Training Intervention:**

Study procedures are outlined in the figure below. After screening, eligible participants complete the online informed consent form and the locator form. The locator form records the participant's home and work telephone, address, email, and the contact information of others who may be able to assist research staff to reach the participant, if needed. This information will be used to prompt participants to join the scheduled interview. Only study staff will have access to this information. Participants will be contacted primarily through email to ask them to complete surveys or to schedule online mock counseling sessions, but we will secondarily use text, calls, letters, and social media direct messaging as reminders. Participants will complete the self-administered baseline instruments using Alchemer software and be scheduled to complete an online mock counseling session.

After both the baseline survey and mock counseling session have been completed, participants will be randomized into one of three groups using a blocked randomization procedure. The block randomization procedure is used to control for level of education (high school/GED, bachelors, masters, PhD) and training and experience in Cognitive Behavior Therapy (CBT) and Applied Behavior Analysis (ABA), as CRAFT is a CBT based on ABA principles.

We will use an additive components design consisting of: 1) digital tutorial only (T), 2) digital tutorial plus digital training materials (TM), and 3) digital tutorial and digital training materials plus feedback and coaching (TMC). This design will allow us to assess whether the digital training materials improve counselor outcomes relative to the tutorial only, but will not allow us to assess their contribution, if any, to the full training product (TMC).

Follow-up assessments will be conducted after all three groups have completed the tutorial (at 2 weeks) and again at 12-weeks post baseline. All aspects of the study will be conducted completely virtually.

Table 1. Treatment Conditions

TREATMENT CONDITION	Pre-tutorial Assessment	Tutorial	Post-Tutorial Assessment	Experimental Manipulation	12-week Follow-up
	Week 0	Week 1-2	Week 2		Week 12
Digital Tutorial (T)	A	Digital Tutorial	B	Weekly emails encouraging review of specific modules and continued use of the online tutorial	C

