### **Aim 2- Training Intervention:**

#### ***Data collected directly from participants:***

Surveys for baseline, post tutorial (i.e., 2-weeks post baseline), and 12-weeks post baseline assessments will be self-administered using Alchemer software since participants may be located anywhere across the country. The baseline survey consists of socio-demographic questions, such as gender, age, race/ethnicity; other standardized socio-demographic measures adapted from the GPRA instrument; a CRAFT Knowledge Test; and a Training Expectations Form.

Each assessment point also will include an audiotaped mock client session conducted via web conferencing with a standardized patient portrayed by a professional actor. Using a standardized patient will provide a consistent context for measuring counselors' CRAFT skill level at each time-point. The mock session will present the counselor with an opportunity to roleplay CRAFT procedure: teaching the CSO to invite the IP to enter treatment (the same procedure is required for the follow-up assessments). We chose to assess this procedure because a component analysis study showed it positively impacted treatment entry rates and it requires CRAFT skill accumulation (i.e., it incorporates and builds upon skills trained in communication and positive reinforcement). Audio tapes will be coded using the CRAFT Therapist Coding Manual used by [name] to certify counselors.

At the post-tutorial and 12-week follow-up assessments additional surveys will be added regarding satisfaction with the training program, perceptions of usefulness and usability, implementation potential, and program value. Finally, at the 12-week follow-up only, participants will be asked to report the number of CSOs they have worked with over the past 10 weeks, how many of them they implemented CRAFT with, and how many of those CSOs had a loved one who entered new treatment. The measures, their purposes, related hypotheses, and assessment points are provided in the **Measures Table** below.

Table 3. Measures

Purpose	Hypothesis	Measure	Assessment points 
Counselor Knowledge and Skill	i. TMC>TM>T	CRAFT Therapist coding Manual***	Pre-Tutorial, Post-Tutorial, 12 weeks
	ii TMC>TM>T	CRAFT Knowledge Test**	Pre-Tutorial, Post-Tutorial, 12 weeks
Acceptability and Feasibility	iii	Training Expectations Form x	Pre-Tutorial
	iii	Training Satisfaction Survey x	Post-Tutorial, 12 weeks

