  - a. **Discomfort associated with being audiotaped during the focus group, individual interviews, or mock or actual sessions.** We will help participants to understand that feeling uncomfortable when being audiotaped is usually transitory. For participants submitting audiotapes of mock or actual client sessions, we will clarify that our goal is to evaluate the training programs, not their abilities per se. If participants experience significant distress such that it makes participation uncomfortable for them, they will be reminded that they can leave the study at any time.
  - b. **Discomfort associated with the training intervention (Aim 2 only)** - The level of distress associated with training interventions is expected to be similar to that which they would experience during any training program and is not a function of the research participation per se. Nonetheless, participants will be informed about this possible risk before consenting and will be told that they can withdraw from the study at any time without penalty. If participants in the TMC condition are experiencing difficulty, discomfort, or distress associated with locating CSOs for actual client sessions, we will help facilitate a client match for them from our We The Village community of family members with a loved one struggling with OUD. If they are experiencing discomfort due to concerns about protecting client confidentiality for those clients participating in videotaped sessions, we will discuss with them steps to ensure client consent and to protect client confidentiality.
3. **Disappointment associated with the training intervention (Aim 2 only)** – It is possible that counselors will be disappointed with the training condition to which they are randomly assigned. Counselors assigned to the T and TM conditions may be disappointed that they did not receive a more intensive training opportunity that would allow them to become certified as CRAFT counselors. Should these individuals wish to pursue CRAFT certification through We The Village after their research participation has ended they will not be charged for the components they have already received and can complete certification at a reduced cost. Counselors who are randomly assigned to the TMC training program may be disappointed that they did not receive a less intensive training program. These individuals, like all study participants, are free to withdraw from the study at any time.

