Cover Page: Statistical Analysis Plan
We The Village Counselor Training Study
NCT05875142
Document Date: 09.26.23

Statistical Analysis Plan

Our statistical analysis focuses on a primary endpoint as well as a number of secondary endpoints of interest. The data derive from questionnaires collected from participants in the study. The final enrollment involved three groups: T – Digital Tutorial Overview, TM – Digital Tutorial Plus Training Materials, and TMC – Digital Tutorial Plus Training Materials Plus Feedback and Coaching, with 15, 16, and 16 subjects enrolled, respectively.

1. **T – Digital Tutorial Overview:** Participants assigned to T were given access to a digital tutorial consisting of a curriculum dashboard for review of 10 modules, including videos, PDFs, text and quizzes, which are to be self-administered over two weeks. Modules remain available during the 10-week post tutorial period. Participants receive weekly contact encouraging engagement in all of the materials available to them.
2. **TM – Digital Tutorial Plus Training Materials:** Participants receive the digital tutorial (T) as described above plus access to 10 modules of digital training materials released weekly over the 10-week post tutorial period for self-study. Participants receive weekly contact encouraging engagement in all of the materials available to them.
3. **TMC – Digital Tutorial Plus Training Materials Plus Feedback and Coaching:** Participants receive the digital tutorial (T) plus the digital Training materials as described in the two arms above plus they submit audio recordings of sessions with clients and receive feedback on their application of CRAFT and coaching on how to improve. Participants receive weekly contact encouraging engagement in all of the materials available to them.

Our comparisons are all treatment/control comparisons of T with TM, and T with TMC.

1. Primary Hypothesis
 - 1.1. At 12 weeks (after study start), participants assigned to the TMC condition will demonstrate the highest CRAFT procedure fidelity (measured in audiotaped sessions with a standardized patient) followed by TM and then T.

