Rationale: Direct observation measuring content of CRAFT delivered in treatment sessions is our primary outcome as this provides the best assessment of counselor adherence and skill and is consistent with previous studies.^{7,10,41} Our hypothesis that TMC will produce greater use of CRAFT than T (or TM) is based on the results from previous trials comparing a workshop only to workshops plus feedback and coaching.^{7,10,41}
2. Secondary Hypotheses
 - 2.1. Participants assigned to the TMC condition will demonstrate the highest CRAFT knowledge followed by TM and then T, in their 12-week knowledge test.
Rationale: Results from previous controlled trials have shown no differences in counselor knowledge pre- to post-workshop, but increases have been seen when fact sheets and supervision are added after the workshop.^{39,57-58}
 - 2.2. Participants in all conditions will perceive increased implementation potential over time (pre-tutorial, post-tutorial, 12 week follow up), but at 12 weeks implementation potential will be lower for TMC compared to TM and T.
Rationale: In a CBT (Cognitive Behavioral Therapy) web-based training study implementation potential of three training programs increased over time, but a condition involving expert supervision was seen as more difficult to implement.³⁹

2.3. Participants assigned to the TMC condition will report that more IPs have entered treatment compared to TM and T at 12-weeks (after study start) follow-up surveys. *Rationale:* This hypothesis is based on the results from previous trials examining counselor fidelity^{7,10,41} and studies showing that CBT fidelity enhances treatment outcome.⁵⁹⁻⁶⁰ *We consider this hypothesis exploratory because the 6 month timeline will not be sufficient to adequately test for differences in treatment entry, as there would not be much time after all counselors completed training for them to complete CRAFT with CSOs.*

Data Analysis

Primary and secondary hypotheses were investigated by computing the improvement from baseline to 12-week timepoints. One-sided independent samples T-tests were used for pairwise comparisons of the three conditions. One-sided tests are appropriate for our hypothesized conditions: the alternative hypotheses for which we seek evidence is TMC is better than T, TM is better than T, and TMC is better than TM.

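### For fidelity and knowledge, the 12-week change-score t-test ignores the week-2 score, can include only counselors with a 12-week score, and is less precise than a baseline-adjusted three-visit mixed model

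*SAP*

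**What the plan says.** The SAP's whole method is in its Data Analysis paragraph: "Primary and secondary hypotheses were investigated by computing the improvement from baseline to 12-week timepoints", followed by "One-sided independent samples T-tests were used for pairwise comparisons of the three conditions". It gives no alpha, analysis set, imputation rule or other treatment of missing scores. Enrolment in T, TM and TMC is reported "with 15, 16, and 16 subjects enrolled, respectively". The number with a 12-week score is not reported.

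The protocol schedules three assessments. Section 4.1 (Aim 2) states: "Follow-up assessments will be conducted after all three groups have completed the tutorial (at 2 weeks) and again at 12-weeks post baseline". Section 4.2 adds: "Each assessment point also will include an audiotaped mock client session". Table 3 lists both the fidelity coding and the knowledge test at "Pre-Tutorial, Post-Tutorial, 12 weeks".

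Under Section 4.1, the baseline survey and mock session must be complete before randomisation, and the arm-specific training occupies the ten weeks after the tutorial. The week-2 score is therefore taken before the training content differs between arms.

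On attrition, Section 9.7 says only that rates will be monitored. Section 9.3 (item 3) says that counselors in T and TM may be disappointed not to get more intensive training, and adds: "Counselors who are randomly assigned to the TMC training program may be disappointed that they did not receive a less intensive training program". It then says that these counselors, like all participants, may withdraw.

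**The concern.** A change score needs both ends. Without an imputation rule, a counselor with no 12-week session contributes nothing, even with baseline and week-2 scores on file. This is inferred from the method and the silence on missing data; the SAP does not say it.

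Two things are at stake.

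- **Precision.** Subtracting the baseline in full is inefficient when the week 0 to 12 correlation is moderate. With 15 or 16 per arm, that loss is material even if nobody drops out.
- **Bias.** If counselors who did poorly after the tutorial leave one arm more than another, the completers differ between arms. The week-2 score shows part of that difference, and the stated analysis does not look at it. If the leavers are weak TMC counselors, the error goes in the direction that the one-sided test looks for.

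**Working it through.** **Inputs.** From the documents: T 15 and TMC 16 enrolled; scores at weeks 0, 2 and 12; one-sided tests. Assumed, because the documents give none: one-sided alpha 0.05, unit SD at each visit, correlations between visits, and dropout. The documents contain no power or precision figure to reproduce. Correlations are written in the order r(0,2) / r(0,12) / r(2,12).

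**Step 1. Precision with no dropout.** Let s = √(1/15 + 1/16) = 0.359.

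- Change score: SE = s√(2(1 − r)), with r = r(0,12).
- Baseline-adjusted: SE ≈ s√(1 − r²).

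| r | Change score | Adjusted, formula | Adjusted, simulated |
|---|---|---|---|
| 0.3 | 0.359 × 1.183 = 0.43 | 0.359 × 0.954 = 0.34 | 0.34 to 0.35 |
| 0.5 | 0.359 × 1.000 = 0.36 | 0.359 × 0.866 = 0.31 | 0.32 |

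For an assumed true effect of 0.8 SD, power is 59% against 75% at r = 0.3, and 72% against 82% at r = 0.5. With complete data, week 2 adds nothing here. A mixed model without the common baseline mean gives the same contrast as the t-test (SE 0.365 in simulation).

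**Step 2. Precision with dropout.** With 4 lost per arm and correlations 0.3/0.3/0.7, the SE is about 0.50 for the change score, 0.40 with baseline adjustment alone and 0.39 to 0.40 with week 2 added. With 20% lost at random in every arm (0.5/0.5/0.7), the figures are 0.405, 0.353 and 0.340. Nearly all the gain is baseline adjustment.

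**Step 3. Bias when dropout depends on week 2 in one arm.** Suppose the k lowest week-2 scorers of 16 leave TMC, k leave T at random, and there is no true effect. The mean week-2 score of the remaining TMC counselors rises by 0.22 SD (k = 2) or 0.40 SD (k = 4), the mean of the top 14 or 12 of 16 normal order statistics. The change score is then biased by

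bias = [r(2,12) − r(0,2)] × rise.

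| Correlations | k = 2 | k = 4 | Simulated type I, t-test |
|---|---|---|---|
| 0.3/0.3/0.7 | 0.4 × 0.22 = +0.09 | 0.4 × 0.40 = +0.16 | 7 to 8%; 9 to 10% |
| 0.3/0.3/0.5 | 0.2 × 0.22 = +0.04 | 0.2 × 0.40 = +0.08 | 6%; 6 to 7% |
| 0.5/0.5/0.7 | +0.04 | +0.08 | 6%; 7% |
| 0.5/0.5/0.5 | 0 | 0 | 5%; 5% |

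Simulated biases agree to within about 0.01 SD. An estimator using all three visits had bias under 0.01 SD in every row.

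**Step 4. Milder dropout.** If TMC dropout is only correlated 0.5 with week 2 (0.3/0.3/0.7, 4 lost per arm), the bias is +0.07 SD and type I error 6.3%. With probabilistic loss of 31% in TMC and 10% elsewhere, the bias is +0.03 to +0.07 SD over four sets of correlations. If all arms follow the same week-2 rule, it is zero.

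**Step 5. Where the three-visit model does not help.** Using the same 31% and 10% losses:

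| Dropout in TMC depends on | t-test bias | Three-visit model, common baseline |
|---|---|---|
| Week-2 score, observed | +0.03 to +0.07 | −0.01 to 0.00 |
| Week-12 score, unseen | +0.10 to +0.25 | +0.11 to +0.28 |
| Week-2 score, lost before week 2 | +0.03 to +0.07 | +0.12 to +0.16 |

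Baseline adjustment without week 2 is also worse than the t-test in the first row at 0.5/0.5/0.7: +0.15 against +0.07. The two parts of the fix belong together.

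**The case against.** A reader might infer that the protocol expects counselors to leave TMC because of client taping and weekly calls, so that the t-test is known to favour TMC. The documents do not support that. Section 9.3 allows for disappointment in both directions, names T and TM first, does not tie withdrawal to taping or calls, and predicts no withdrawal. Sections 4.1 and 5.1 describe reminders by several routes and a gift card for each assessment session in every arm. Actual dropout could be zero.

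The upper bias figures also need the weakest TMC counselors to leave with certainty while T loses people at random. Every bias in Steps 3 and 4 is small beside standard errors of roughly 0.3 to 0.5.

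Other objections stand in part.

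- The arms diverge after week 2, so dropout caused by the coaching itself need not be predictable from week 2. Step 5 shows no rescue there, and a worse result for dropout before week 2.
- Including all 47 is partly nominal. Counselors with only a baseline add almost nothing to the contrast, and data deleted under Section 4.3 for late-found ineligibility cannot be recovered.
- The simulations used an equivalent regression estimator without covariates or the small-sample correction, so type I error of the full recommended model was not checked.
- The SAP is written in the past tense. Changing the main analysis now is a post hoc choice.
- A baseline-to-12-week contrast does answer a hypothesis stated at 12 weeks.

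These points limit the claim. They leave untouched the precision loss, the unused visit and the absent missing-data rule.

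**Conclusion.** The point holds as an improvement the plan should make; it does not show that the result is biased. The reasonably secure part is precision: a standard error of about 0.35 instead of 0.43 SD, or 0.31 instead of 0.36 SD, if the week 0 to 12 correlation is 0.3 or 0.5. Almost all of that comes from baseline adjustment.

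The conditional part is bias: about 0 to +0.16 SD, with one-sided type I error from 5% to about 9.5%, if 2 to 4 counselors are lost per arm and TMC losses follow week-2 skill while T losses do not. Week 2 removes this component only. A reader might take the mixed model as a general cure for dropout; it is not, because it relies on data being missing at random given arm, baseline and week 2. The correlations, alpha and dropout are all assumed.

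**What to change.** For fidelity and knowledge, estimate TMC−T, TM−T and TMC−TM at week 12 from a mixed model with weeks 0, 2 and 12 as responses, one common mean at week 0, arm-by-visit terms afterwards, unstructured covariance and Kenward-Roger degrees of freedom. Week 2 is then a response, so the model does not adjust for a post-randomisation covariate. Include every randomised counselor in the assigned arm.

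Keep randomisation covariates few. The means take 1 + 2 × 3 = 7 parameters and the covariance 6. Four education levels plus yes/no CBT and ABA experience would add 5, making 18 for 47 people.

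Report 12-week missingness by arm, split into before and after week 2. Report the change-score t-test alongside, and label the mixed model as added after the SAP. State that it assumes data missing at random, does not correct dropout before week 2 or dropout driven by unseen later progress, and gains little from baseline-only counselors. If losses differ by arm, add a sensitivity analysis for data not missing at random.

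Limit the change to these two outcomes: treatment entry is collected only at 12 weeks, and Table 3 lists implementation potential only post-tutorial and at 12 weeks.

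The cost is SAP wording and one model per outcome on data already scheduled for collection, plus the reduced standing of an analysis chosen after the plan was written.

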  - 2.3. Participants in all conditions will perceive increased implementation potential over time (pre-tutorial, post-tutorial, 12 week follow up), but at 12 weeks implementation potential will be lower for TMC compared to TM and T.

*Rationale:* In a CBT (Cognitive Behavioral Therapy) web-based training study implementation potential of three training programs increased over time, but a condition involving expert supervision was seen as more difficult to implement.
  - 2.4. Participants assigned to the TMC condition will assign the highest monetary value to the tutorial, digital training and certification components, followed by TM and then T participants, in their 12-week follow-up surveys.

*Rationale:* The pilot study of our CRAFT Family product showed participants assigned to the CRAFT private coaching condition valued all components of the program substantially higher than those who received less coaching in the group condition, or digital only (no coaching) condition.
  - 2.5. Participants assigned to the TMC condition will report that more IPs have entered treatment compared to TM and T at 12-weeks (after study start) follow-up surveys.

*Rationale:* This hypothesis is based on the results from previous trials examining counselor fidelity and studies showing that CBT fidelity enhances treatment outcome. *We consider this hypothesis exploratory because the 6 month timeline will not be sufficient to adequately test for differences in treatment entry, as there would not be much time after all counselors completed training for them to complete CRAFT with CSOs.*

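### The SAP's blanket one-sided rule that TMC is better contradicts its own hypothesis 2.2, which predicts TMC lower on implementation potential, and the documents disagree on whether that scale has a baseline

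*SAP*

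**What the plan says.** The SAP's Data Analysis paragraph sets a single analysis for everything. On the variable: "Primary and secondary hypotheses were investigated by computing the improvement from baseline to 12-week timepoints". On the test: "One-sided independent samples T-tests were used for pairwise comparisons of the three conditions". On direction: "the alternative hypotheses for which we seek evidence is TMC is better than T, TM is better than T, and TMC is better than TM". No endpoint is exempted.

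SAP hypothesis 2.2 (hypothesis 2.3 in Protocol section 1.2) concerns implementation potential and makes two claims. The first is a rise within every arm: "Participants in all conditions will perceive increased implementation potential over time (pre-tutorial, post-tutorial, 12 week follow up". The second is a difference between arms: "at 12 weeks implementation potential will be lower for TMC compared to TM and T". The rationale given is that an earlier training study found the supervised condition harder to put into practice, so lower means less favourable.

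On collection, Protocol section 4.2 lists the baseline survey as demographics and "other standardized socio-demographic measures adapted from the GPRA instrument; a CRAFT Knowledge Test; and a Training Expectations Form". It places the implementation scale among the later surveys: "post-tutorial and 12-week follow-up assessments additional surveys will be added regarding satisfaction with the training program, perceptions of usefulness and usability, implementation potential". The Implementation Potential Scale row of Table 3 shows post-tutorial and 12 weeks only. The note to that table names a baseline counterpart for the satisfaction survey and for no other instrument.

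On which pairs are compared, the SAP's opening section says: "Our comparisons are all treatment/control comparisons of T with TM, and T with TMC".

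**The concern.** A one-sided test answers only the question its alternative asks. If the alternative is that TMC is better and the hypothesis is that TMC is lower, a true effect in the hypothesised direction can appear only as a non-significant result. A significant TMC comparison would be evidence against the hypothesis under test. With about 16 people per arm, the choice of tail can decide the result. A reader given a p-value for this endpoint could not tell which tail, which variable or which pairs produced it.

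The SAP reports final enrollment and describes its tests in the past tense. If the tail was chosen by endpoint without being written down, it could be read as chosen after the data were seen.

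**Working it through.** **1. Direction, side by side**

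| Pair | Alternative in Data Analysis | SAP hypothesis 2.2 |
|---|---|---|
| TMC v T | TMC better | TMC lower |
| TMC v TM | TMC better | TMC lower |
| TM v T | TM better | no direction given |

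Two of the three stated alternatives are opposite to 2.2, and 2.2 is silent on the third. For fidelity (1.1) and knowledge (2.1) the hypothesised order is TMC, then TM, then T, which matches the stated alternatives. For treatment entry (SAP 2.3, labelled exploratory) the direction also matches.

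**2. Baseline, side by side**

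| Source | Time points for implementation potential |
|---|---|
| SAP 2.2 and Protocol 2.3 | pre-tutorial, post-tutorial, 12 weeks |
| Protocol 4.2, baseline survey contents | scale not listed |
| Protocol 4.2, follow-up surveys | post-tutorial, 12 weeks |
| Protocol Table 3 | post-tutorial, 12 weeks |

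On the scheduled measures, change from baseline cannot be computed. The documents do not settle whether the scale was in fact given at Week 0. Fidelity and knowledge are scheduled at all three time points, so the change score exists for both.

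**3. Pairs.** Hypothesis 2.2 needs TMC v TM as well as TMC v T. The SAP's opening section allows only T v TM and T v TMC; Data Analysis tests all three.

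**4. Within-arm claim.** The predicted rise over time in all conditions is a within-arm statement. Between-arm t-tests do not address it.

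**5. Size of the direction error (illustration).** Neither document gives an alpha, SD, effect size or power, so there is no figure to reproduce. Inputs: T 15, TM 16 and TMC 16 from the SAP. Assumed: alpha 0.05, no dropout, equal variances, 12-week scores compared, TMC truly lower by d SDs of that score.

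The t statistic has df = n1 + n2 − 2 and noncentrality d × √(n1·n2/(n1 + n2)). For TMC v T, df = 16 + 15 − 2 = 29 and √(240/31) = 2.782. At d = 0.5 the noncentrality is 1.391, against a one-sided critical value of 1.699.

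| Comparison | d | Stated alternative (TMC better) | Hypothesised alternative (TMC lower) | Two-sided 0.05 |
|---|---|---|---|---|
| TMC v T, 16 v 15 | 0.3 | 0.69% | 20% | 13% |
| | 0.5 | 0.13% | 39% | 27% |
| | 0.8 | 0.007% | 70% | 58% |
| TMC v TM, 16 v 16 | 0.5 | 0.12% | 40% | 28% |
| | 0.8 | 0.006% | 71% | 59% |
| TMC v T, 13 v 12 | 0.5 | 0.21% | 33% | 22% |
| | 0.8 | 0.017% | 62% | 48% |

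The 13 v 12 rows assume 20% dropout (0.8 × 16 = 12.8, 0.8 × 15 = 12). For 80% power, one-sided 0.05, in the hypothesised direction, the difference must be about 0.92 SD (16 v 15) or 0.90 SD (16 v 16).

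**6. If a baseline does exist.** With equal SDs and baseline-to-week-12 correlation r, the standardized difference in change is d/√(2(1 − r)). For d = 0.5 and assumed r of 0.3, 0.5 and 0.7 this is 0.42, 0.50 and 0.65. The stated tail then rejects 0.26%, 0.13% and 0.03% of the time, and the hypothesised tail 31%, 39% and 54% (16 v 15). The direction problem remains either way.

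**The case against.** The best defence is that the SAP presents its one-sided alternatives as those suited to its hypotheses, which could mean that each test follows its own hypothesis. But the sentence goes on to list the alternatives, and none has TMC lower. If endpoint-specific tails were intended, one added sentence would say so.

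A second objection is that the baseline conflict may be only a scheduling omission. Two hypothesis statements name a pre-tutorial measurement, and Table 3 carries symbols whose key is not in the available text. This part stands: it supports a query to the authors and does not show that the scale was never given at Week 0. If it was given, the change score can be computed and, for r above 0.5, is more powerful than the 12-week score. Even so, 2.2 is worded as a 12-week level, and that score is available on every reading.

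Third, treatment entry is asked about at 12 weeks only, and only for clients with whom the counselor used CRAFT. Participants must not have been trained in CRAFT before the study, so the baseline count is arguably zero and change equals the 12-week count. That is fair. For this endpoint the mismatch is one of wording.

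Fourth, the stated TM v T alternative contradicts nothing, since 2.2 is silent on that pair. This is true, but 2.2 then gives no ground for testing it one-sided on this endpoint.

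Finally, the conflict over pairs reaches fidelity and knowledge too and could be raised separately. It belongs here only because 2.2 cannot be tested without TMC v TM. The power figures rest on assumptions and should not raise the severity.

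**Conclusion.** The concern holds. The direction conflict is plain on the text and does not depend on any calculation. Under the assumptions above, if 2.2 is true with a difference of 0.3 to 0.8 SD, the stated TMC v T test rejects between 0.69% and 0.007% of the time, against 20% to 70% in the hypothesised direction. Correcting the tail still leaves a weak test at this sample size. The baseline conflict also holds as a conflict between passages; which passage is right cannot be told from the documents.

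The direction error affects one of the SAP's three secondary hypotheses. The baseline problem affects the same one and, in wording, the exploratory treatment-entry endpoint. Neither touches the primary outcome or knowledge. This should be fixed, but it does not threaten the pilot's main result.

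**What to change.** State the analysis variable and the alternative for each endpoint.

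- **Implementation potential, between arms:** test the 12-week score with the alternatives already hypothesised, TMC below T and TMC below TM, or two-sided. Report TM v T two-sided or descriptively.
- **Implementation potential, within arm:** use a paired comparison over the time points actually collected. If there is no Week 0 score, say that post-tutorial to week 12 does not cover any rise before the post-tutorial survey.
- **Fidelity, knowledge and treatment entry:** keep the direction that TMC is better. Analyse treatment entry on its 12-week value, still labelled exploratory.
- **Reconcile:** confirm which surveys were given at Week 0, and bring the hypothesis wording into line with Protocol section 4.2 and Table 3. Settle whether two or three pairs are compared before TMC v TM is tested.
- **Record:** date the change, cite hypothesis 2.3 in Protocol section 1.2 as the source of the direction, and label the change post hoc if data had been seen.

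The cost is SAP wording and a check of the Week 0 surveys. If the tests have already been run, a few t-tests must be repeated and a reporting note added. No new data are needed.
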